9.1.1 GENERAL

Descriptive statistical methods will be used to summarize the data from this study with hypothesis testing performed for primary and secondary endpoints. These include number of subjects (n), mean, median, standard deviation, minimum, and maximum for continuous data, and frequencies and percentages for categorical data. All data collected during the study will be reported and analyzed.

Unless specified otherwise, all statistical testing will be two-sided and performed using a significance (alpha) level of 0.05.

All statistical analyses will be conducted using PASW 19.

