9.2 RESEARCH HYPOTHESES

Primary endpoints

H1: Time to heal

Time to heal after 12 weeks of CelluTome™ + SOC (**Group 1A**; maximum of 3 CelluTome™ applications) versus 12 weeks of SOC (**Group 2B**) will be equal for both groups or time to heal after 6 weeks of CelluTome™ + SOC (**Group 1A**; maximum of 2 CelluTome™ applications) versus 6 weeks of SOC (**Group 2A**) will be equal for both groups. Formally, $H_0: T_1 - T_2 = 0$; $H_A: T_1 - T_2 = D_1 \neq 0$, where T_1 is the time to heal for **Group 1A**, T_2 is the time to heal for **Group 2A or 2B** depending whether T_2 is 12 or 6 weeks, D_1 is the difference ($T_1 - T_2$) assuming the alternative hypothesis, and statistical test used is log rank applied to a Kaplan-Meier analysis. If either result is statistically significant, results will be adjusted using Cox regression and appropriate covariates.

Secondary endpoints

H2: Proportion of wounds healed

The proportion of wounds healed at 12 weeks after 12 weeks of CelluTome™ + SOC (**Group 1A**; maximum of 3 CelluTome™ applications) versus 12 weeks of SOC (**Group 2B**) will be equal for both groups. Formally, $H_0: P_1 - P_2 = 0$; $H_A: P_1 - P_2 = D_1 \neq 0$, where P_1 is the proportion of wounds healed for **Group 1A**, P_2 is the proportion of wounds healed for **Group 2B**, D_1 is the difference ($P_1 - P_2$) assuming the alternative hypothesis, and statistical test used is chi square.

H3: Incidence of Adverse Events (AEs)

The incidence of adverse events (AEs) by 12 weeks after 12 weeks of CelluTome™ + SOC (**Group 1A**; maximum of 3 CelluTome™ applications) versus 12 weeks of SOC (**Group 2B**) will be equal for both groups. Formally, $H_0: I_1 - I_2 = 0$; $H_A: I_1 - I_2 = D_1 \neq 0$, where I_1 is the incidence of AEs for **Group 1A** on a per subject basis, I_2 is same metric for **Group 2B**, D_1 is the difference ($I_1 - I_2$) assuming the alternative hypothesis, and statistical test used is the Mann-Whitney test.

H4: Correlation of wound area with protease activity at 4 weeks

The Pearson correlation coefficient (or Spearman's rho in the case of severe non-normality) calculated

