The first hypothesis to be tested is that the proportion of wounds healed in **Group 2C** (12 weeks of SOC + 2 CelluTome™ applications) is no more than 15% lower than the proportion of wound healed in **Group 2B** (12 weeks of SOC). Noninferiority is established if the lower limit of the $(1 - 2\alpha) \times 100\%$ CI (confidence interval) for the difference (**Group 2C** – **Group 2B**) is above -15% where the equivalence margin, δ , is 15%. If non-inferiority is not established because the proportion of wounds healed in **Group 2C** is much higher than in **Group 2B**, the superiority hypothesis testing used in H2 will be utilized.

H8: Incidence of Adverse Events (AEs) (Groups 2B versus 2C)

The incidence of adverse events (AEs) by 12 weeks after 12 weeks of CelluTome™ + SOC (**Group 2C**; maximum of 2 CelluTome™ applications) versus 12 weeks of SOC (**Group 2B**) will be equal for both groups. Formally, $H_0: I_1 - I_2 = 0$; $H_A: I_1 - I_2 = D_1 \neq 0$, where I_1 is the incidence of AEs for **Group 2C** on a per subject basis, I_2 is same metric for **Group 2B**, D_1 is the difference ($I_1 - I_2$) assuming the alternative hypothesis, and statistical test used is the Mann-Whitney test.

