9.3 SAMPLE SIZE CALCULATIONS

A two-sided logrank test with an overall sample size of 225 subjects (113 in the control group and 112 in the treatment group) achieves 86.1% power at a 0.05 significance level to detect a hazard ratio of 1.74 when the proportion of wounds healed in the control group is 0.5. The study lasts for 12 weeks with all subjects beginning the study together (no accrual periods). The proportion dropping out of the control group is 0.033 per week. The proportion dropping out of the treatment group is 0.0083 per week. The proportion switching from the control group to another group with a hazard ratio equal to that of the treatment group is 0.

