- Proportion of wounds healed at 12 weeks will be analyzed by chi square (unadjusted); this endpoint may also be analyzed using logistic regression to adjust for the following variables (with and without covariate imputation) if needed:
 - Site
 - Year enrolled (if trial lasts 2 years or more)
 - Treatment group
 - Initial area at randomization (cm²)
 - Initial wound depth (cm)
 - Age of wound at enrollment (days)
 - Smoking status
 - Prior VLU
 - Pain score at randomization

- Patient age
- Gender
- Ethnicity/race
- VCS score
- Diabetes
- Patient on pain medications
- Smoking status
- BMI
- Infection episodes

Note: unadjusted testing for **Group 2C** versus **2B** will be non-inferiority, followed by superiority testing if the former fails and proportion of wounds healed in **Group 2C** is much higher than in **Group 2B**.

- A summary of the incidence of adverse events (count by patient):
 - AE (category)
 - SAE (category; brief description; resolution; should include death)
 - When event happened in relation to start of treatment (days)
 - Associated patient ID, site ID

Incidence of AEs will be analyzed by Mann-Whitney test on a per subject basis.

- Correlation of changes in wound area with changes in protease activity will be first analyzed by calculating the Pearson correlation coefficient for each group or Spearman's rho if data are grossly non-normal. For each subject the change in protease activity is calculated by subtraction of the value at 4 or 8 weeks from the value at baseline; reduction in wound area is calculated similarly. Differences in r will be analyzed using Steiger's Z test with the assumption that r will have the same sign for both groups. If significant differences are found between groups, further analysis using GLM doubly multivariate repeated measures (change in wound area and protease activity between baseline and 4 and 8 weeks) to adjust for the following variables (with and without covariate imputation) may be undertaken (ordinal re-categorization will be done if data are severely non-normal):
 - Site
 - Year enrolled (if trial lasts 2 years or more)
 - Treatment group
 - Initial area at randomization (cm²)
 - Initial wound depth (cm)
 - Age of wound at enrollment (days)
 - Smoking status
 - Prior VLU
 - Pain score at randomization
 - Patient age
 - Gender
 - Ethnicity/race
 - VCS score

CELLUTOME™ IN VENOUS LEG

- Diabetes
 - Patient on pain medications
 - Smoking status
 - BMI
 - Infection episodes

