- SAE (Poisson distribution variable, count at patient level; date of onset; resolution; brief description)

ADJUSTMENT FOR FEWR

Adjustment to control for the family wise error rate (FEWR) (also known as multiplicity of testing) will use the Hochberg step-up procedure thus: Let $p_1 \geq p_2 \geq \dots \geq p_K$ be the ordered p-values and H_1, H_2, \dots, H_K be the corresponding null hypotheses. Reject H_k and all H_j for $j \leq k$ if $p_k \leq \alpha/k$. The adjusted p-values are $p_{adj,k} = \min \{p_1, 2p_2, \dots, kp_k\}$ for $k = 1, 2, \dots, K$.

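### Adverse-event tests H3 and H8 give no estimate or confidence interval for excess harm, and the Hochberg family is left undefined, so its natural reading also adjusts the harm tests

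*Combined protocol and SAP*

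**What the plan says.** Section 9.1.1 calls for "hypothesis testing performed for primary and secondary endpoints" and sets the default: "all statistical testing will be two-sided and performed using a significance (alpha) level of 0.05". AE incidence is a secondary outcome in section 3.

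In section 9.2, H3 begins "The incidence of adverse events (AEs) by 12 weeks after 12 weeks of CelluTome™ + SOC" and sets a null of equal incidence in Groups 1A and 2B. The same null is set for Groups 2C and 2B under "H8: Incidence of Adverse Events (AEs) (Groups 2B versus 2C"). Both name the Mann-Whitney test, and section 9.7 repeats it: "Incidence of AEs will be analyzed by Mann-Whitney test on a per subject basis". No effect measure, interval, margin or power is given for AEs. H7, on healing, does have a margin (15%) and a confidence interval.

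On multiplicity, section 9.7 states: "Adjustment to control for the family wise error rate (FEWR) (also known as multiplicity of testing) will use the Hochberg step-up procedure thus". The ordered p-values run from largest (p_1) to smallest (p_K). The text does not say which hypotheses make up the K.

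Other safety material is descriptive or uses absolute thresholds:
- a review of infections and withdrawals in the first 40 subjects (9.5);
- interim AE and SAE counts, with 25% triggers for infection and ulcer deterioration (9.6);
- an AE/SAE summary by category and timing (9.7);
- tabulation and comparison of AEs by arm (10.1).

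**The concern.** The trial is meant to evaluate safety as well as effectiveness. A test of equality that fails to reject says little about safety unless the reader can also see which excesses the data rule out. Nothing planned shows that. The 25% infection trigger, for example, would not be met with 12% in one group and 24% in the other, although the rate has doubled.

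Multiplicity adjustment limits false claims of benefit. Applied to harm tests it works the wrong way: it raises AE p-values and makes a non-significant result easier to reach. A real excess of AEs with grafting could then appear in the report only as a non-significant p-value.

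**Working it through.** **1. The plan's own figure.** Power is stated only for time to heal. Section 9.3 says that with 225 randomised (113 control, 112 treated) the planned log-rank comparison "achieves 86.1% power at a 0.05 significance level to detect a hazard ratio of 1.74". With 50% of controls healed at 12 weeks, the control hazard is ln 2/12 = 0.0578 per week, and the treated hazard is 1.74 × 0.0578 = 0.1005. With weekly dropout of 0.033 and 0.0083, expected events are about 47.6 + 75.4 = 123. Schoenfeld: √(123/4) × ln 1.74 − 1.96 = 1.11, which gives 86.7% power. A Lakatos-type calculation gives 85.7% and Freedman's formula 85.0%. The stated 86.1% is reproduced. No comparable figure exists for H3 or H8.

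**2. Group sizes.** Section 5.1 expects 30% of Group 2A to switch: 0.3 × 113 ≈ 34 in 2C, leaving 79 in 2B. H3 is therefore 112 vs 79, and H8 is 34 vs 79. After 10% dropout these are about 101 vs 71 and 31 vs 71.

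**3. Threshold.** If H1-H8 form the family, K = 8 and the strictest Hochberg step is 0.05/8 = 0.00625. If H1 counts as two tests it is 0.05/9 = 0.00556. The strictest step applies when the AE p-value is the smallest and no other hypothesis passes its own step. Otherwise the threshold lies between it and 0.05.

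**4. Power for a doubled AE count.** Simulated Mann-Whitney on Poisson counts (section 9.7 defines AEs as a Poisson count per patient). The control means are assumptions. Each cell shows power at 0.05 / at 0.05/8.

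| Control mean | H3, 112 vs 79 | H3, 101 vs 71 | H8, 34 vs 79 | H8, 31 vs 71 |
|---|---|---|---|---|
| 0.1 | 39% / 12% | 35% / 11% | 28% / 8% | 25% / 8% |
| 0.2 | 67% / 36% | 62% / 29% | 43% / 19% | 40% / 16% |
| 0.5 | 96% / 85% | 95% / 80% | 76% / 48% | 75% / 45% |

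If counts are overdispersed (negative binomial, k = 0.5, control means 0.05 to 1.0), H3 power is 16-59% at 0.05 and 2-28% at 0.05/8. H8 power is 18-36% and 4-13%.

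**5. Power for a doubled proportion with any AE, after dropout.** From 10% to 20%, H3 has 42% power at 0.05 and 15% at 0.05/8; H8 has 30% and 11%. From 30% to 60%, H3 has 98% and 89%; H8 has 82% and 55%. Running the full Hochberg procedure with the other seven hypotheses null gives H3 16% at 10% to 20%; with three of the seven well powered it gives 18%.

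**6. What an interval would show.** The half-width is 1.96 × √(p₁(1−p₁)/n₁ + p₂(1−p₂)/n₂). With 10% in both groups after dropout, it is 9.1 points for H3 (101 vs 71) and 12.7 points for H8 (31 vs 71). For 1A vs all of 2A as randomised (112 vs 113) it is 1.96 × √(0.09/112 + 0.09/113) = 7.8 points.

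**7. The rejection rule.** Section 9.7 makes p_1 the largest p-value, then rejects H_k together with every H_j for j ≤ k, which are the hypotheses with larger p-values. Take two illustrative values, p_1 = 0.60 (an AE test) and p_2 = 0.01 (healing). Since 0.01 ≤ 0.05/2, the printed rule rejects both. The section's own adjusted-p formula gives 0.60 for the first and min(0.60, 2 × 0.01) = 0.02 for the second, so it rejects only the second. The two statements conflict; j ≥ k makes them agree.

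**The case against.** Four points against the concern deserve weight.

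- **Safety is not judged by p-values alone.** A reader might infer from 9.2 that it is. The summaries and triggers in 9.5, 9.6, 9.7 and 10.1 show otherwise. The gap concerns formal between-group inference only.
- **Inclusion of H3 and H8 in the Hochberg family is not stated.** The indices H_1 to H_K in 9.7 label ordered p-values, not the hypotheses named H1 to H8 in 9.2. Inclusion is the natural reading, because H3 and H8 sit among the secondary hypotheses and nothing is exempted. It is still a reading; the certain defect is that the family is undefined.
- **A doubling of AEs would not necessarily be missed.** That depends on an AE rate the documents do not give. AEs are defined broadly in 10.1 and elicited by direct questioning, so they may be common, and Poisson H3 power is then adequate.
- **Hochberg is not the main cause.** At 10% to 20%, H3 has 42% power with no correction. Small groups and an uncommon outcome drive the misses, and the correction adds to them. Exempting the tests would not be enough.

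The documents also never say that a non-significant AE test means equal safety. All of this narrows the point. It does not supply the missing estimate and interval, or define the family.

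**Conclusion.** The concern holds in this form. H3 and H8 are the only formal between-group safety inference. They test equality without an estimate or interval, and the undefined Hochberg family leaves them exposed to adjustment.

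If AEs are uncommon (control mean 0.1 to 0.2 per subject), a doubling would often be non-significant even uncorrected, and more often after correction. If they are common (0.5 or more), H3 is adequate under Poisson counts, though not under the overdispersion tried; H8 remains weaker because 2C is small. These figures assume the AE rates shown, 30% switching, a true doubling and, for the lower power figures, the strictest Hochberg step. SAEs and infections, if rarer than AEs overall, are where the problem is greatest.

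A reader might also infer that adding intervals to H3 and H8 would bound the excess harm of grafting. The documents do not support that. Groups 2B and 2C are separated after randomisation by area reduction at TV7 (sections 4 and 6.3), so neither contrast is as randomised. The 12-week AE count in 2C also includes six weeks before any graft.

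This is a cheap improvement that should be made.

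**What to change.** In section 9.7:

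1. List the Hochberg family explicitly as efficacy hypotheses only, excluding H3 and H8.
2. Change the rejection rule to all H_j for j ≥ k, so that it agrees with the adjusted-p formula.
3. Report AEs, SAEs and index-ulcer infections separately, as between-group differences with unadjusted two-sided 95% confidence intervals.
4. Make the as-randomised comparison, 1A vs all of 2A, the main safety contrast, at least over the first 6 weeks before switching. Label 1A vs 2B and 2C vs 2B as non-randomised and descriptive.
5. State that a non-significant AE test is not evidence of equal safety.

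The cost is SAP wording and a few lines of output from data already collected, with no extra patients or procedures. The downside is that each unadjusted safety comparison carries a 5% chance of a false alarm.

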10 ADVERSE EVENTS (DEFINITIONS AND REPORTING)

The Investigator is responsible for the detection and documentation of events meeting the criteria and definition of an AE or SAE, as provided in this protocol. During the study when there is a safety evaluation, the Investigator or site staff will be responsible for detecting, documenting and reporting AEs and SAEs as detailed in this Section of the protocol.

10.1 ADVERSE EVENTS

An adverse event (AE) is defined as any unfavorable or unintended sign, symptom, or disease that occurs or is reported by the patient to have occurred, or a worsening of a pre-existing condition. An adverse event may or may not be related to the treatment regimen. All AEs and intercurrent illnesses must be recorded in the subject's medical records and on the CRF.

Adverse events will be defined as those events that occur after signing the informed consent until the final study visit. A description of the AE along with the onset date, end date, severity, action taken, treatment, outcome, likely cause, and relationship to the study products will be recorded in the CRF.

Local and systemic AEs associated with each treatment arm will be tabulated and compared. AEs will be elicited through direct questioning, subject reports, and physical examination.

An abnormal laboratory test result is not by itself considered to be an AE unless the Investigator considers the finding of clinical significance that should be reported in such a manner.

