	
CelluTome™ system at TV1, TV5 and TV9, visits plus SOC (multi-layer compression) (Group 1A) (2) SOC alone (Group 2A).
 
At TV 7, wound assessment will be carried out to evaluate wound healing in Group 2A. Subjects in Group 2A, whose percentage area reduction (PAR) is <40% will be allowed to have CelluTome™ treatment in addition to continuation of SOC and will constitute Group 2C. Group 2C subjects will receive a graft at TV7 and TV11. The remainder of Group 2A subjects will be termed Group 2B subjects. Patient codes will still remain the same to enable tracking continuity.
 
During the Treatment Phase, the wound will be swabbed for protease activity for Group 1A and 2A/B subjects: TV1 (In Group 1A this will be prior to CelluTome™ application), TV5 and TV9 visits.
 
Subjects will be evaluated on a weekly basis during the Treatment Phase. Effectiveness evaluations each week will include Investigator assessment of wound healing and measurements of ulcer size using digital planimetry. At TV4 and TV8, Prisma™ is to be applied to the study ulcer for Group 1A, 2A, and 2B subjects. Group 2C subjects will receive Prisma™ at TV10. Safety evaluations during the Treatment Phase will consist of adverse event assessments at each visit.

Dosage and Frequency of Administration
	
Epidermal grafting will be applied up to three times in Group 1A: TV1, TV5 and TV9. Group 2C subjects will receive up to two grafts: TV7 and TV11.

Duration of Study
	
A run-in period of 2 weeks followed by 12 weeks of active treatment.

Statistical Methods, Power, and Sample Size Calculations
	
Please see the Statistical Analysis Plan in the protocol.

Protease Levels
	
Absolute values of inflammatory proteases (Neutrophil elastase, MMP 8 and 9) will be measured at S1 before application of Prisma™, day 0 before application of Epidermal grafts and week 4 and 8 visits thereafter to determine the effect of protease levels on graft success for Group 1A and 2A/B subjects. The results will be blinded to the Investigators.

Key Words
	
Epidermal Grafts Chronic Wounds Clinical Trial Venous Leg ulcer Protease levels in chronic wounds

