2.4 EPIDERMAL BLISTER GRAFTING

Epidermal grafts have been used to treat acute and chronic wounds for decades. However, in the past epidermal micrografts were created using a free hand blade or syringes which applied negative pressure to produce an epidermal blister.^{23,24,25,26,27,28,29} However, these procedures are difficult to perform, can remove dermis resulting in patient discomfort and can be time consuming. The CelluTome™ epidermal harvesting system (Acelity, San Antonio, TX) is cleared by the FDA and commercially available in the United States. It harvests up to 120 epidermal blister grafts from a donor site usually on the inner thigh. The grafts are collected in a dressing that can easily be transferred to another area of the body. To date, this system has been used to treat acute and chronic wounds in Haiti and across the United States.^{30,31} The results from these case series suggest that epidermal grafting is effective in accelerating the healing in VLUs. In fact, the principal investigator's experience suggests that epidermal grafting may be far superior to current advanced therapies. The epidermal harvesting procedure is described in section 19.7.

Epidermal results in minimal or no discomfort to the patient. Anesthesia is not required. The donor site heals in 3 to 4 days. In the principal investigators case series experience the only adverse event seen was irritation of the donor site secondary to the Tegaderm® dressing.³¹ These adverse events resolved with

removal of the Tegaderm®. There were no problems with donor site healing. Epidermal grafting is associated with a low risk of complications and potentially can accelerate closure of venous ulcers.

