6.1 VISIT WINDOWS

Subject visit dates must be scheduled within the visit windows detailed on the Schedule of Events tables. One week equals 7 days.

During the Screening Phase, each visit is scheduled from the S1 visit date, with reference to the allowed visit window.

During the Treatment Phase, each visit is scheduled from the TV1 visit date, with reference to the allowed visit window. For example, the TV2 visit is scheduled for 1 week \pm 2 days after the TV1 visit. TV3 is scheduled for 2 weeks \pm 2 days after the TV1 visit.

SCHEDULE OF EVENTS

Visit	SVs (14 days)	TV1 (rand)	T V	TV3	TV4	TV5	TV6	TV7	TV8	TV9	TV10	TV11	TV12- 13
Weeks from Randomization Date			+1	+2	+3	+4	+5	+6	+7	+8	+9	+10	+11-12
Window Period	0		±2 da	±2 days	±2 days	±2 days	±2 days	±2 day	±2 days	±2 days	±2 days	±2 days	±2 days
Assessment of eligibility	√												
Medical history	√												
Apply Prisma™	√				√				√		√ ^[B]		
Randomization		√											
Ulcer assessments	√		√	√	√	√	√	√	√	√	√	√	√
Physical exam	√												
Vital signs	√												
Pain assessment	√		√	√	√	√	√	√	√	√	√	√	√
Study ulcer photographs	√		√	√	√	√	√	√	√	√	√	√	√
Study ulcer cleaning	√		√	√	√	√	√	√	√	√	√	√	√
Study ulcer debridement	√ ^[A]		√	√	√	√	√	√	√	√	√	√	√
Study ulcer swab	√	√				√				√			
Assessment of compression bandaging	√		√	√	√	√	√	√	√	√	√	√	√
Epidermal graft application		√				√		√ ^[B]		√		√ ^[B]	
Study ulcer dressings and compression therapy	√	√	√	√	√	√	√	√	√	√	√	√	√
Study ulcer closure assessment			√	√	√	√	√	√ ^[C]	√	√	√	√	√
Assess for concomitant medications	√	√	√	√	√	√	√	√	√	√	√	√	√
Assess for AEs and SAEs		√	√	√	√	√	√	√	√	√	√	√	√
Quality of Life, PBI-P and Time-trade off questionnaires		√				√				√			√ ^[D]

[A] – If required per the Investigator’s judgment.

[B] – **Group 2C** subjects only

[C] – Evaluation of wound area reduction since TV1. Subjects in **Group 2A** (SOC), whose study ulcer PAR is < 40%, will become **Group 2C**; the remainder of **Group 2A** subjects will become **Group 2B**

[D]- Questionnaires are to be completed for TV13 only

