6.2 SCREENING PHASE

The subject will sign and date the ICF and HIPAA authorization (according to site practices) prior to any study-related procedures. A screening number will be assigned to each subject in successive order of entering the study after signing the ICF at each center, beginning with 001 at each site.

SCREENING VISIT – S1

The following procedures must be performed:

- Informed consent will be obtained prior to any study related procedures and the subject will sign a written Informed Consent Form
- Demographic information will be collected.
- Medical history obtained.
- Concomitant medications assessed.
- Vital signs taken.
- Physical examination performed.
- Pain assessment.
- Ulcer history recorded.
- Study Ulcer Assessments will be recorded.
- Assess signs and symptoms of clinical infection of the study ulcer.
- Vascular assessment.
- Clean the study ulcer using saline.
- Digital photo of the study ulcer.
- Perform swab on study ulcer.
- Debridement of the study ulcer if applicable.
- Application of Prisma™ or allowed antimicrobial dressing (Appendix 19.8).
- Apply multi-layer compression bandaging therapy.
- Assessment of subject's eligibility to continue on in the study.
- Schedule the next visit (S2 or TV1) in one week, if they are still eligible.

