6.3 TREATMENT PHASE

TREATMENT VISIT 1 (TV1) – PRIOR TO RANDOMIZATION

The following procedures must be performed:

- Pain assessment

CELLUTOME™ IN VENOUS LEG

- Assess effectiveness of compression bandaging
- Check for any changes in the subject's health and update the Medical History with any changes
- Assess concomitant medications
- Assessment of study ulcer
- Check for signs of clinical infection of the study ulcer.
- Clean the study ulcer with saline.
- Digital photo of the study ulcer
- Debridement, if required to remove non-viable tissue
- If the subject is eligible, perform the following procedures (TV1) immediately.
- If the subject is not eligible, discharge the subject from the study as a screen failure.

TREATMENT VISIT (TV1) – RANDOMIZATION

- Randomize the subject
- Perform swab on study ulcer
- If randomized to the epidermal grafting arm: Harvest epidermal grafts using the CelluTome™ device then apply the grafts to the wound bed. (Procedure detailed in Appendix 10).
- If randomized to standard of care apply provided foam to the ulcer.
- Apply multi-layer compression therapy
- Complete Quality of Life, PBI-P, and Time trade off questionnaires (see Appendices 19.5, 19.6, and 19.2)
- Schedule the next study visit one week later

TREATMENT PHASE VISITS TV2-4, 6, 8, 10, 12

The following procedures must be performed:

- Pain assessment
- Assess compression bandaging
- Assess concomitant medications
- Check for any changes in the subject's health and update the Adverse Events or Serious Adverse Events pages with any events
- Study ulcer closure assessment will be determined by a blinded observer
 - If the study ulcer is 100% re-epithelialized, the subject will be scheduled for a Pre-Healing Confirmation Visit (HCV) one week later
 - If the study ulcer is healed, no other study procedures need to be completed at this visit
- Check for signs of clinical infection. If clinical diagnosis of infection has been made, then the subject can be treated with topical antimicrobials or oral antibiotics, but topical antibiotics CANNOT be used on the study ulcer. During the time that an infection is being treated,

CELLUTOME™ IN VENOUS LEG

treatment with the IP will be stopped.

- Digital photo of the study ulcer
- Apply Prisma™ or approved antimicrobial dressing at TV4, TV8 for both **Groups 1A/2A,2B**; and at TV10 for **Group 2C**.
- Apply provided foam and multi-layer compression bandaging therapy.
- The next visit will be scheduled for one week.

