19.10 EPIDERMAL HARVESTING PROCEDURE

- Select donor site (inner thigh).
- Using clippers to remove any hair from the skin. (Do not use a razor to shave the patient)
- Prep the site with isopropyl alcohol.
- Anesthesia is not required.
- Apply the harvester and affix in place using the Velcro strap.

[figure not shown]

- Attach the vacuum hood. Press on the opposite sides of the hood until you here a click. This ensures that you have a seal.

- Turn the machine on. The vacuum head will apply 200 mmHg negative pressure and heat the skin to 40 C. The patient may experience a warm feeling.
- The epidermal microdomes are ready for harvesting when the epidermis has formed blisters as shown.

[figure not shown]
CELLUTOME™ IN VENOUS LEG

- Turn off the power.
- Remove the vacuum hood.
- Place the foam dressing provided in the harvester.

[figure not shown]

- Pull the blue handle back until you hear a “click.”
- Place the foam dressing provided in the harvester. Activate the blades cutting the epidermal microdomes by advancing the blue handle back onto the harvester.

CELLUTOME™ IN VENOUS LEG

- Examine the foam and record the percentage of microdomes harvested.

- Transfer the foam to the wound and secure using the 3M Coban-2 compression wrap.

- Cover the donor site with Tegaderm® provided.

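### Section 10.1 counts physical examination among the ways adverse events are found, but after screening none is scheduled and no visit includes a donor-site check

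*Combined protocol and SAP*

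**What the plan says.** Section 10.1 names three routes of detection: "AEs will be elicited through direct questioning, subject reports, and physical examination". It also promises that local and systemic events will be tabulated and compared by arm.

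In the Schedule of Events (section 6.1) the row "Physical exam" is ticked in the screening column only. Section 6.2 lists "Physical examination performed" at S1, and no list in section 6.3 repeats it. The row "Assess for AEs and SAEs" is ticked from TV1 to TV12-13, and the synopsis adds: "Safety evaluations during the Treatment Phase will consist of adverse event assessments at each visit". From TV2 onward, the visit lists ask staff to check for changes in health and "update the Adverse Events or Serious Adverse Events pages with any events". No body site is named.

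On the donor site, section 2.4 reports that in the case series "the only adverse event seen was irritation of the donor site secondary to the" film dressing, and that these events resolved when the dressing was removed. Appendix 19.10 places the donor site on the inner thigh and ends with the instruction "Cover the donor site with Tegaderm". Nothing after that asks for the site to be looked at or its state recorded.

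**The concern.** The study ulcer is examined weekly in both arms, including for signs of infection (section 8.7.2). The wound created by harvesting exists only in grafted subjects, and no scheduled procedure covers it. One of the three detection routes in section 10.1 therefore has no counterpart in the post-randomization schedule beyond the study ulcer, and the gap falls on one side of the comparison.

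Safety is a stated aim of the design (section 4). H3 compares adverse-event incidence between Groups 1A and 2B, and H8 between Groups 2C and 2B. An unrecorded donor-site event lowers the count in 1A or 2C and cannot lower it in 2B. The trial is open-label, so blinding does not offset the uneven ascertainment.

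**Working it through.** The plan states no figure to reproduce. The check has two parts.

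**Comparison of sections**

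- Physical examinations scheduled after randomization (Schedule of Events; section 6.3): 0.
- Visit lists or schedule rows naming the donor site: 0.
- Donor-site items among the variables required for the final analysis (section 9.7): 0. The interim list in section 9.6 asks for a separate category for infected wounds but none for the donor site.
- General adverse-event assessment: every schedule column from TV1 to TV12-13.
- Occasions when staff would handle a possible donor area again: repeat harvests, four weeks apart (TV1, TV5, TV9 in Group 1A; TV7, TV11 in Group 2C). Section 2.4 gives donor-site healing as 3 to 4 days.

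**How many harvests this covers**

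Inputs: 112 treated and 113 control subjects, control healing 0.5 at 12 weeks, hazard ratio 1.74 and treated-arm dropout 0.0083 per week (section 9.3); 30% of Group 2A switching to 2C (section 5.1); up to three grafts in Group 1A and two in Group 2C (synopsis). I assume a constant weekly hazard and a graft at each scheduled visit while the ulcer is open.

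- Treated hazard per week: 1.74 × ln 2 / 12 = 0.1005.
- Proportion still open: exp(−0.1005 × 4) = 0.669 at week 4; exp(−0.1005 × 8) = 0.448 at week 8.
- Group 1A harvests: 112 × (1 + 0.669 + 0.448) = 237. With dropout: 112 × (1 + 0.669 × 0.9917⁴ + 0.448 × 0.9917⁸) = 231.
- Group 2C subjects: 0.30 × 113 = 34. Harvests: 34 × 2 = 68 if all receive both, or 34 × 1.669 = 57 if they heal at the treated rate.
- Total: 231 + 57 = 288 to 237 + 68 = 305, or roughly 290 to 305.

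Incidental viewing at a repeat harvest cannot follow a subject's last harvest. There is one last harvest per grafted subject, 112 + 34 = 146, about half of the total.

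One sentence in section 4 describes a single application at day zero for Group 1A, which conflicts with the synopsis and schedule. Read that way, the total would be 112 + 57 = 169 to 112 + 68 = 180. The conclusion does not depend on which count applies.

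**The case against.** The strongest reply is that the plan already has active surveillance. Section 10.1 lists direct questioning separately from subject reports, adverse events are assessed at every visit, and section 10 makes the investigator or site staff responsible for detection. This stands. A reader might infer that donor-site harm is recorded only if the subject raises it, and the documents do not support that.

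A reader might also infer that the donor wound is never seen. That goes too far as well. Each repeat harvest requires staff to select and prepare an inner-thigh site, which under the counts above happens about 125 times in Group 1A (237 − 112) and 23 to 34 times in Group 2C. This is weak cover: it is unplanned, comes four weeks later, and does not occur in subjects who have healed.

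Section 2.4 should not be read as saying that irritation is the one harm specific to grafting. It reports what was seen in a case series.

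The adverse-event form is not in the documents. Section 10.1 requires a description of each event and section 9.7 a category, so location may already be recoverable. It cannot be said that the form lacks it.

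The physical examination in section 10.1 could be meant as the weekly ulcer examination. If so, the text should say so, and the donor site remains outside it.

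**Conclusion.** The point holds as a gap in safety ascertainment. Section 10.1 names a route of detection that the treatment-phase schedule supplies only for the study ulcer, and the wound made by the intervention has no structured check. The primary endpoint is unaffected.

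Any under-recording would favour grafting in H3 and H8. Whether that moves a result toward or away from no difference depends on the other adverse events: it is toward the null if grafted subjects truly have more events, and away from it if they have fewer.

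The size can be given only as exposure, roughly 290 to 305 harvests under the assumptions above. The number of missed events cannot be estimated, because the documents give neither a reaction rate nor a reporting rate.

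A reader might take the gap to mean that the plan fails to test the 3 to 4 day healing time. That figure is background rather than an objective, and a check at 7 ± 2 days would not test it either.

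**What to change.** 1. Add a donor-site observation to the Schedule of Events and section 6.3, at the existing weekly visit after each harvest: TV2, TV6 and TV10 for Group 1A; TV8 and TV12 for Group 2C. Record site closed (Y/N), irritation (Y/N) and signs of infection (Y/N).
2. State that it is completed even when the study ulcer is found healed at that visit. The visit lists otherwise waive the remaining procedures, and section 6.4 treats the subject as having completed the study.
3. Make sure that adverse-event location (study ulcer, donor site, other) is captured, so that the local and systemic tabulation in section 10.1 can be produced.
4. In section 9.7, report donor-site events per subject and per harvest, with 95% confidence intervals that allow for repeated harvests within a subject. The allowance matters. With zero events, the one-sided 95% upper limit is 1 − 0.05^(1/237) = 1.3% if 237 harvests are treated as independent, but 1 − 0.05^(1/112) = 2.6% per subject.
5. Reconcile section 10.1 with the schedule, so that physical examination refers to something that is done.

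The cost is one schedule row, a few form fields and about a minute at visits that already take place. More mild events will be recorded in grafted subjects, making the graft safety figures look somewhat less favourable. No treatment changes.
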